## **2. AIMS/OBJECTIVES/HYPOTHESES**

### **Aims/Objectives**

To evaluate the effects of the personalised health care program which includes care plans, escalation process and tele-health on:

- ED admissions
- Acute Admissions
- LOS on acute admission
- Self-reported GP appointments
- To understand the effects of a model of care on health literacy and self-management
- To assess appropriate outcome measures for a fully powered randomised controlled trial
- To assess the variability of outcome measures to aid in sample size calculation for a fully powered randomised controlled trial
- Recruitment and retention rates
- Compliance with self-reporting
- Qualitative Interview
- Survey

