#### **5. RECRUITMENT**

All patients identified as meeting the selection criteria will be sent a letter regarding the pilot study with some information regarding the pilot study and what would be required of a participant. A reply paid envelope will be provided which includes preferred date, time and best method of contact; those interested to participate could indicate this and return to the research team. The program staff with administration support provided with this contact information (i.e. home, mobile phone, email). Responders interested in participation will be followed up by phone and an appointment arranged to meet and discuss the pilot study and their possible participation and appointment arranged if possible. Appointment reminders will be sent along with any pertinent information such as the PDCF prior to agreed time

Non-responders will also be followed up by sending a follow up invitation 2 weeks after the initial invite, The second invite will refer to the first and will highlight that there is a "not interested response" section. Any patient who chooses not to participate in the pilot at this stage will not be contacted again. Rolling enrolment will occur and over a period of 6 months. As patients are enrolled patients will be randomised to the control or intervention arms of the pilot. This gradual recruitment aims to recruit 200 individuals in the intervention group and 200 in the control group. Please see the statistical analyses section for detail on randomisation method

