**Data Storage/Record Retention**

Data	Pre and post measures of	Intervention	Control	Monitor only	Program Evaluation	Source
Length of Stay (LOS)	LOS or average LOS(s) at hospitalisation	✓	✓	✓	✗	Data Ware-House

Hospital Admissions	Number of hospitalisations in past 12 months	✓	✓	✓	✗	Data Ware-House	F v f c E f
ED Presentations	Number of ED presentations in past 12 months	✓	✓	✓	✗	Data Ware-House	F v f c E f
Quality of Life	Specific validated questionnaire	✓	✓	✗	✗		F v f c E f
Health Literacy \ Self management	Specific validated questionnaire	✓	✓	✗	✗		F v f c E f
Mortality		✓	✓	✓	✗	Hospital Data	F v f c E f
PRaDA	Predictive value of the patients (intervention vs control vs followed)	✓	✓	✓	✗	PRaDA	F v f c E f
Interviews	NA	✗	✗	✗	✓	Word files/PDF password	

						protected
--	--	--	--	--	--	-----------

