**Statistical analyses**

**Sample size**

This study is a pilot intended to gather information surrounding the efficacy and feasibility of the

intervention, and has not been powered to detect any (minimal) clinically relevant difference between the intervention and control arms. Sample size has been guided by available resources and funding.

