### **Methods**

Due to the pilot nature of the study, analysis of study data will not follow a hypothesis testing framework. Confidence intervals for efficacy outcomes will be calculated within each group at the 95% confidence level, however no formal significance tests will be made. Hospital admissions will be treated as a binary variable, ED presentations as counts, and LoS as ordinal. Total LoS (summed over all admissions) will be presented.

Allowances for stratification of the sample will be made via the Cochran–Mantel–Haenszel (CMH) test for unadjusted analyses, and adjustment for covariates will further be investigated via logistic regression for binary variables; adjustment for covariates will use Poisson regression for count variables. Analysis of the readmission rates will further be summarised under a time-to-event framework.

Baseline measures will be summarised by group, as will any differences post-intervention. Trial procedures (such as recruitment and retention rates, compliance and monitoring loads) will be monitored and summarised by confidence intervals where appropriate.

Following verbatim data transcription of each interview, a constant comparative thematic analysis method will be used. Two researchers will analysis the data independently and confer to confirm the thematic structure of the data.

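### Poisson regression is named for the adjusted ED presentation counts with no allowance for over-dispersion; if variance exceeds the mean, its model-based intervals would be too narrow

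*Protocol*

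**What the plan says.** The Methods part of section 10 assigns a scale to each utilisation outcome: "Hospital admissions will be treated as a binary variable, ED presentations as counts, and LoS as ordinal". For the adjusted analysis it then states that "adjustment for covariates will use Poisson regression for count variables". The table under Data Storage/Record Retention defines the ED measure as "Number of ED presentations in past 12 months", so each patient contributes a total that includes repeat visits.

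On intervals, Methods states: "Confidence intervals for efficacy outcomes will be calculated within each group at the 95% confidence level". It does not say how the interval for a count is to be obtained. It also rules out formal significance testing.

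The Aims/Objectives list includes this one: "To assess the variability of outcome measures to aid in sample size calculation for a fully powered randomised controlled trial". The protocol nowhere mentions over-dispersion, a scale parameter, robust variance, a negative binomial model or an offset for follow-up time.

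**The concern.** A Poisson model takes the variance of the count, given the covariates, to equal its mean. That would need patients with the same covariates to share nearly the same visit rate, and visits by one patient to be independent of each other. This population is selected for high admission risk and combines COPD with Type I and Type II diabetes. Some patients are likely to attend the ED often and others not at all. Observation time may also differ: participants can leave, continued non-compliance ends participation, and deaths are recorded.

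If the residual variance exceeds the mean, the usual Poisson standard error does not respond, and the interval for the adjusted comparison claims more precision than the data hold. Because the pilot makes no formal tests, estimates and intervals are what readers will use to judge the effect on ED presentations, the first outcome listed in the aims.

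**Working it through.** **Inputs from the protocol.** The recruitment target is to "recruit 200 individuals in the intervention group and 200 in the control group". The confidence level is 95% and follow-up is 12 months. The sample size has no statistical derivation ("Sample size has been guided by available resources and funding"), so there is no power figure to reproduce.

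**Inputs not in the protocol, assumed here.** These are the mean ED count per patient (set to 1.0 where needed) and the ratio φ = variance/mean, varied from 1 to 3. For an adjusted model, φ is what remains after the covariates.

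**Step 1: coverage.** With n per arm and means m₁ and m₂, the Poisson standard error of the log rate ratio is √(1/(n·m₁) + 1/(n·m₂)). With a common φ the true standard error is √φ times this. A nominal 95% interval therefore covers with probability 2Φ(1.96/√φ) − 1, where Φ is the standard normal distribution function. This does not depend on n or on the mean.

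**Step 2: interval width.** At n = 200 per arm and mean 1.0, the Poisson standard error is √(2/200) = 0.100. The interval runs from the rate ratio divided by, to the rate ratio multiplied by, exp(1.96 × 0.100 × √φ). The Poisson model gives exp(0.196) = 1.22 whatever φ is.

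| Assumed φ | √φ | Coverage of Poisson interval | Correct 95% factor |
|---|---|---|---|
| 1 | 1.00 | 95.0% | 1.22 |
| 1.25 | 1.12 | 92.0% | exp(0.219) = 1.25 |
| 1.5 | 1.22 | 89.0% | 1.27 |
| 2 | 1.41 | 83.4% | 1.32 |
| 3 | 1.73 | 74.2% | 1.40 |

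**Step 3: simulation.** Gamma-Poisson counts were simulated with 200 per arm, mean 1.0 and no covariates, with 5,000 runs for each φ.

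| φ | Poisson coverage | Robust coverage | Mean Poisson SE | Mean robust SE | Mean sample variance/mean |
|---|---|---|---|---|---|
| 1 | 94.9% | 94.8% | 0.100 | 0.100 | 1.00 |
| 1.5 | 89.3% | 95.0% | 0.100 | 0.122 | 1.49 |
| 2 | 83.0% | 94.6% | 0.100 | 0.141 | 1.99 |
| 3 | 74.1% | 94.9% | 0.100 | 0.172 | 2.97 |

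The formula is confirmed. The robust variance restores coverage, and it costs almost nothing when φ = 1. The raw variance-to-mean ratio recovers φ.

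**Step 4: what the protocol's own risk range implies.** The eligibility criteria admit predicted 12-month admission risks of 0.5 to 0.8. Suppose, for illustration, that these were Poisson risks of at least one event. The rates −ln(1 − p) would then run from 0.69 to 1.61. A uniform spread of p gives a mean rate of 1.082 and a variance between patients of 0.067, so φ = 1 + 0.067/1.082 = 1.06. This concerns admissions rather than ED visits. It shows that a large φ would have to come from heterogeneity that the protocol does not quantify.

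**The case against.** Four counter-arguments carry weight.

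- **The variance estimator is open.** The protocol names Poisson regression but does not say model-based standard errors. A SAP, not available here, could specify robust or scaled variance without contradicting it. This is true and lowers the severity. It does not remove the point, because the protocol fixes the model and asks for no check of its main assumption.
- **The promised 95% intervals are within each group.** Poisson regression is named only for covariate adjustment. This stands. The coverage figures apply to an interval from the adjusted comparison, if one is reported, and not to the within-group intervals, whose method for counts is unstated.
- **The size is assumed.** No ED mean or variance is given, covariates may absorb part of the heterogeneity, and Step 4 alone yields only 1.06. This also stands, so the finding has to be conditional.
- **Little is decided on this interval.** The pilot "has not been powered to detect any (minimal) clinically relevant difference between the intervention and control arms" and makes no formal tests, so no type I error or decision rule is affected.

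A reader might go further and infer that the variability handed to the definitive trial is understated, so that trial would be too small. The documents do not support this. Assessing variability is an aim in its own right, and no section says that it will come from the Poisson model. Methods plans summaries by group, and Step 3 shows that an ordinary sample variance recovers the dispersion. What can be said is narrower: Poisson regression does not itself estimate dispersion, and the protocol does not commit to reporting it for the counts.

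**Conclusion.** The point holds in conditional form. The protocol fixes Poisson regression for adjusted ED counts and makes no provision for variance above the mean, which repeat visits by high-risk patients make likely. If model-based standard errors are used and φ lies between 1.25 and 3, actual coverage of a nominal 95% interval would be about 92% down to 74%, and the interval on the log scale should be 1.12 to 1.73 times as wide. At φ = 1 nothing is wrong. These φ values are assumptions, and the documents neither confirm nor exclude them. No claim is made about the size of the later trial. This should be fixed, but it does not threaten the pilot: the point estimates and the feasibility outcomes are not affected by it.

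**What to change.** In Methods, replace the Poisson statement for counts with negative binomial regression, or with Poisson regression using robust (sandwich) standard errors. In either case include log follow-up time as an offset. To serve the variability aim in section 2, add that the mean, variance and estimated dispersion of ED counts will be reported by arm.

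This takes a sentence or two and uses the ED counts already planned, together with each participant's length of observation. The price is wider intervals if over-dispersion is present. If it is absent, the simulation at φ = 1 shows practically no loss with the robust variance (coverage 94.8%, standard error 0.100).

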### **Baseline Initial assessment and at 12 months - measures and observations**

Diabetes cohort

- Diabetes Type I or II
- HR, Rhythm
- Blood Pressure
- current HbA1c
- Serum Lipids
- Urine micro albumin
- Weight/height (BMI)
- Summary of health status including complications
- Medications including adjustment regime
- Validation/quality control of individual meter documented
- AQoL
- Health Education Impact Questionnaire
- Interview
- Survey

COPD cohort

- Recent lung function test
- HR, Rhythm
- Blood Pressure
- Weight/height (BMI)
- Barwon Health Respiratory Initial Health Assessment Tool
- 6 min walk test
- Mental health screen (K10)
- COPD Assessment Test (CAT)
- Summary of health status including complications

- Medications including adjustment regime
- AQoL
- Health Education Impact Questionnaire
- Interview
- Survey

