**10. OUTCOMES AND SIGNIFICANCE**

**Statistical Analyses**

**Sample Size (n=400)**

In similar models of care operating, one nurse monitors approximately 100 patients. In line with this, our proposed service model aims to provide proof of concept for this approach. The funding provided by the Department of health to operate the pilot model of care, is specified for 200 patients over a period of 18 months. Therefore the “*Intervention Group*” sample size will be a maximum of 200. The “*Control Group*” will also be 200 in order to monitor comparative changes.

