**Allocation method**

Individuals will be allocated by a stratified minimisation randomisation algorithm. Stratification variables will be the individual’s primary diagnosis (COPD/diabetes), and the baseline PRaDA risk of readmission in the following 12 months. The risk strata will consist of four evenly spaced risk sets (0.60-0.65, 0.65-0.70, 0.70-0.75, 0.75-0.80). The minimisation algorithm will be implemented within the study’s enrolment database.

Individuals agreeing to involvement in the study, and who are subsequently allocated, will be assigned a (sequential) allocation number; the combination of the screening number and the allocation number (for example, XXXXX-XXX) will give the unique individual study number. A master file containing individual UR, name, date of birth and study number will be stored separate to other study documents. This allocation and randomisation process will be guided and performed by [name] (Barwon Health Statistician\ Research Fellow)

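### Continuous scores taken at 0 and 12 months get only group summaries: no stated between-arm estimate uses the baseline score or the minimisation factors

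*Protocol*

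**What the plan says.** Under Baseline Initial assessment and at 12 months, the protocol schedules the AQoL and the "Health Education Impact Questionnaire" in both disease cohorts. HbA1c is listed for the diabetes cohort only. The COPD Assessment Test (CAT), K10 and 6-minute walk are listed for the COPD cohort only. The Study Plan confirms that questionnaires are taken at 0 and 12 months in both arms. Health literacy and self-management are objectives, and the Synopsis adds clinical measures.

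Allocation is by minimisation on primary diagnosis and "the baseline PRaDA risk of readmission in the following 12 months".

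Methods gives a model by outcome type: CMH with logistic regression for binary outcomes, Poisson regression for counts, and a time-to-event summary for readmission. Baseline and follow-up scores get this: "Baseline measures will be summarised by group, as will any differences post-intervention". Efficacy confidence intervals are set within each group, and "no formal significance tests will be made".

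One listed aim is this: "To assess the variability of outcome measures to aid in sample size calculation for a fully powered randomised controlled trial". The protocol does not say which SD (raw, change or residual) is meant.

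**The concern.** The trial is randomised, so the informative quantity for each score is the difference between arms. Methods does not describe that difference for continuous scores, and separate within-arm summaries invite a before-and-after reading of the intervention arm. If a reader contrasts the two summaries anyway, the contrast ignores information already in hand. Any chance imbalance in baseline scores passes into it, and the factors used in minimisation are left out.

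Two things are at stake. One is the precision of the descriptive estimates for the health literacy, self-management, quality-of-life and clinical objectives. The other is what the pilot hands on to a full trial: a raw SD alone does not tell its designers how much a baseline-adjusted analysis would save.

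**Working it through.** **The plan's own figure.** The only size given is 400, as 200 + 200. It follows from funded places and from no formula: "Sample size has been guided by available resources and funding". There is no alpha, power, effect or SD behind it to reproduce.

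**Inputs.**
- n = 200 per arm, from Sample Size (n=400). It is a maximum for the intervention arm, and the "Control Group" is set to match.
- 95% confidence level, from Methods.
- SD = 1 at both times (assumed, so results are in SD units).
- rho, the baseline to 12-month correlation: not in the protocol, so assumed over 0.3 to 0.8.

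**Formulas.** Variance per participant, in SD² units:
- 12-month score alone: 1
- change from baseline: 2(1 − rho)
- ANCOVA on baseline: 1 − rho²

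The half-width of the 95% CI for the arm difference is 1.96 × √(2 × variance / n). At n = 200 this is 0.196 × √variance.

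**Direction.** The 12-month-only variance exceeds the ANCOVA variance by the factor 1/(1 − rho²). For change scores the factor is 2(1 − rho)/[(1 − rho)(1 + rho)] = 2/(1 + rho). Both are above 1 for every rho strictly between 0 and 1.

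**Size at 200 per arm.**

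| rho | Variance ratio, 12-month score to ANCOVA | Variance ratio, change to ANCOVA | Half-width, 12-month score | Half-width, change | Half-width, ANCOVA |
|---|---|---|---|---|---|
| 0.3 | 1.10 | 1.54 | 0.196 | 0.232 | 0.187 |
| 0.5 | 1.33 | 1.33 | 0.196 | 0.196 | 0.170 |
| 0.7 | 1.96 | 1.18 | 0.196 | 0.152 | 0.140 |
| 0.8 | 2.78 | 1.11 | 0.196 | 0.124 | 0.118 |

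At rho = 0.5 the adjusted interval is 1 − 0.170/0.196 = 13% narrower.

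**Fewer participants.** With an assumed 20% loss (160 per arm) and rho = 0.5, the half-widths are 0.219 SD unadjusted and 0.190 SD adjusted. For a measure taken in one disease cohort, an assumed even split gives 100 per arm. The half-widths are then 1.96 × √(2/100) = 0.277 SD and 0.277 × √0.75 = 0.240 SD. The protocol does not state the diagnosis split.

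**Minimisation factors.** If diagnosis and PRaDA risk explain a share R² of the outcome variance, leaving them out overstates the standard error by 1/√(1 − R²) − 1. That is about 1% at an assumed R² of 0.02 and 12% at 0.20.

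**The case against.** **This may sit in the SAP.** The model for continuous scores in a pilot is often left to the SAP, which is not at hand. So the absence of ANCOVA here does not prove that none is planned. But Methods is not silent: it assigns models to other outcome types, assigns these scores a group summary, and places the intervals within groups. That is a stated analysis that can be improved.

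**Differences may mean change from baseline.** The wording allows it, and baseline would then be partly used. At high rho this recovers much of the loss (a ratio of 1.11 at 0.8). It does not remove it at any rho below 1, and at rho below 0.5 change scores are worse than 12-month scores alone.

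**CMH might cover the strata.** A generalised CMH mean-score statistic can handle scored outcomes by stratum. It still gives no baseline-adjusted estimate.

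**The study is a pilot without tests.** It "has not been powered to detect any (minimal) clinically relevant difference". This stands against any argument from lost power: no powered comparison exists to be harmed. It does not stand against an interval estimate, which suits a non-testing plan.

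**Stronger readings to avoid.** A reader might infer that the definitive trial will be sized on too large a variance. The protocol does not say so. It does not say which SD will be carried forward, and both time points are collected, so the residual SD and rho can be computed. A reader might also apply the 200-per-arm figures to every score. They cannot hold for HbA1c, CAT, K10 or the 6-minute walk, each scheduled in one cohort only.

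**Conclusion.** The point holds as a should-change on analysis choice. For continuous scores taken at 0 and 12 months, the protocol describes group summaries and within-group intervals, and no between-arm estimate that uses the baseline score or the minimisation factors. The variance penalty against a baseline-adjusted contrast runs from 1.10 to 1.96 for 12-month scores, and from 1.54 down to 1.18 for change scores, as rho goes from 0.3 to 0.7. The direction is certain for rho between 0 and 1. The size depends wholly on a correlation that the protocol does not give, on equal SDs at the two times, and on how many participants are retained.

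Oversizing of a full trial is a risk only. It needs that trial to have a continuous primary outcome, to be analysed by ANCOVA, and to be sized on the raw SD. Under those conditions the excess would be the same 1/(1 − rho²), or 1.33 at rho = 0.5. It would not apply to admissions, ED presentations or length of stay, which Methods treats as binary, count and ordinal.

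**What to change.** In Methods, replace the group summary of post-intervention differences, for continuous scores, with text such as:

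> AQoL and Health Education Impact Questionnaire scores at 12 months, and continuous clinical measures taken in both disease cohorts, will be compared between arms by ANCOVA adjusting for the baseline value, primary diagnosis and PRaDA risk. Continuous clinical measures taken in one disease cohort only will be compared within that cohort, adjusting for the baseline value and PRaDA risk. Adjusted mean differences with 95% confidence intervals will be reported without significance tests, together with the residual SD and the baseline to 12-month correlation for sizing a full trial.

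Diagnosis is left out of the cohort-specific models because it has no role there. Group summaries can stay as description. If a SAP already specifies this, Methods should say so and agree with it.

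The cost is a few sentences in Methods. The covariates and both assessments are already scheduled, so no extra participants, visits or staff are needed.

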### **General Practitioner (GP) COMMUNICATION STRATEGY**

Agency/Agency type	Message	Mode	Time
Medicare Local	Outline of model Update on progress	BH/ Medicare local partnership meetings	Quarterly
Medicare Local	Learning's to date. Demonstration of system with Care-plans	Forum	
Individual GP's- identify all GP's that have clients on MOC	Present an Overview of the model of care	Forum or individual contact via letter/email/phone	
Individual GP's	Printed copy of care- plans mailed to individual GP's following client consent	Mail/email. Any question follow up with phone call	As per client enrolment
Individual GP	Notification of any hospital admission from team	Method of communication to be defined as "usual	As required

		process” being upon discharge a summary with associated clinical result.	
Individual GP’s	Notify of discharge from service	Mail with above	Per client discharge
Medicare Local & individual GP’s involved in patient care	Project findings	Forum	

